- 5.3. A power analysis with G*Power 3.1.9.2 software indicates that n=30 is sufficient in the context of a t-test to detect a difference between groups for the primary outcome that is roughly equal to the sample standard deviation. For (purely hypothetical) example, if the mean is 100 units and roughly 2/3 of the sample falls between 95 and 105, we would have 80% power to detect a treatment difference of 5 units.

6. Study Timelines

- 6.1. All data collection will occur in conjunction with clinically-indicated surgical care. The existence of this study will not affect the decision to refer for surgery, or the subsequent decision to proceed or not proceed with surgery, for any patient.
 - Data collection will include pre-operative serum creatinine levels, which are very likely to already have been recorded for clinical reasons. The maximum pre-operative interval for this value will be six months (it is extremely unlikely that sufficiently recent serum creatinine data will be unavailable, but if this is the case, this value will be obtained prior to surgery). Other data will be gathered immediately prior to surgery, immediately after surgery, and up to 48 hours postoperatively. It is anticipated that all participants will already be in the hospital for all data collection.
 - A recruitment period duration of one year should be sufficient to recruit the targeted participant sample; we will apply for continuing review prior to study expiration if the target sample size is not met at that time.

The Impact of Low Chloride Containing Fluids on Acute Kidney Injury after Cardiopulmonary Bypass as Assayed by Urinary [TIMP2]*[IGFBP7]

- Upon completion of data collection, the investigators anticipate one year for completion of all analyses, manuscript/presentation preparation, and submission of scholarly product to relevant outlets.

7. Study Endpoints

7.1. The primary outcome is the change in urinary [TIMP2]*[IGFBP7] composite from baseline to 24 hours postoperatively.

The secondary outcomes are:

- serum creatinine preoperatively and postoperatively at 24 and 48 hours,
 - serum chloride preoperatively and postoperatively at 24 and 48 hours,
 - clinically-determined need for dialysis prior to discharge, and
 - arterial pH, measured 24 hours after surgery.

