- 13.1. The primary outcome involves a composite index: the product of urinary TIMP2 and IGFBP7 values. For a given patient, this index will be calculated for preoperative values and for postoperative values as described above, and the difference between pre- and postoperative index values will be recorded as the primary outcome. A t-test (or Wilcoxon-Mann-Whitney test, in the case of nonnormal distributions) will be used to evaluate the hypothesis. Secondary outcomes that similarly involve pre- vs. postoperative changes in laboratory values (serum creatinine and serum chloride) will be tested in the same fashion. The 24-hour arterial pH data will be assessed with t-test or Wilcoxon-Mann-Whitney as appropriate depending on distribution normality. The clinically-determined need for dialysis prior to discharge will be assessed with Fisher's Exact test.
- 13.2. A power analysis with G*Power 3.1.9.2 software indicates that this sample size is sufficient in the context of a t-test to detect a difference between groups for the primary outcome that is roughly equal to the sample standard deviation. For (purely hypothetical) example, if the mean is 100 units and roughly 2/3 of the sample falls between 95 and 105, we would have 80% power to detect a treatment difference of 5 units.

14. Provisions to Monitor the Data to Ensure the Safety of Subjects

- 14.1. Both normal saline and Isolyte have been used routinely in cardiac procedures for many years, nationally and at UNMHSC, and both have excellent safety records. The PI [name] and co-investigators will conduct an interim review of patient records upon completion of data collection for the 20th participant, in an effort to detect substantial differences in outcomes.
- 14.2. All study data will be reviewed.
- 14.3. Both normal saline and Isolyte have been safely used in cardiac surgery for many years. It is exceedingly unlikely that scientific literature would indicate a substantial difference in risk posed by these two solutions; however, as Chief of Cardiac Anesthesia at UNMH, [name] routinely reviews scientific/medical literature related to cardiac surgery.
- 14.4. Patient records will be reviewed for unusual patterns of morbidity/mortality. In addition, all outcomes will be analyzed with the above-described statistical tests.

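### The creatinine comparison in 13.1 has no rule for values drawn after dialysis starts, so early kidney failure can enter as a small or negative rise.

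*Combined protocol and SAP*

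**What the plan says.** Section 7.1 lists the secondary outcomes separately. The creatinine outcome reads "serum creatinine preoperatively and postoperatively at 24 and 48 hours". Chloride has the same three sampling times. The dialysis outcome is given as "clinically-determined need for dialysis prior to discharge". The remaining item in the list is worded "arterial pH, measured 24 hours after surgery".

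Section 13.1 gives each its own test. For creatinine and chloride: "Secondary outcomes that similarly involve pre- vs. postoperative changes in laboratory values (serum creatinine and serum chloride) will be tested in the same fashion". The reference is to the primary outcome's method, a t-test, or Wilcoxon-Mann-Whitney if the data are not normal, on the pre-to-post difference. The 24 h pH values are compared between arms by the same pair of tests. For dialysis: "The clinically-determined need for dialysis prior to discharge will be assessed with Fisher's Exact test".

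Nothing connects the dialysis outcome to the laboratory outcomes. Section 12.1 has the need for dialysis recorded but lists no date or time for it. The data-omission rules in 15.1 to 15.4 concern problems while the fluids are being given and participant withdrawal. Section 4.2 excludes patients on dialysis, or about to need it, at enrolment. That does not reach dialysis started after surgery.

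**The concern.** Section 12.1 says the outcomes are meant to show kidney injury or the risk of it. Creatinine does this only while the kidneys alone are clearing it. Once dialysis has started, the measured value partly reflects the treatment. A plan that takes the 24 or 48 h value as recorded can therefore give a patient with one of the worst renal courses in the trial a small or negative creatinine rise. The resulting bias in the creatinine comparison favours the arm that patient is in.

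With 15 patients per arm, one such value carries weight. The problem would also be hard to repair afterwards. Sections 16.6 and 16.7 say that data are de-identified and not coded, and that forms bearing identifiers are shredded once the data are entered. If no start time has been captured by then, the study dataset cannot show which values followed dialysis, and not even a post-hoc sensitivity analysis would be possible.

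**Working it through.** **Inputs from the documents.** 30 completers, 15 per arm, allocated 1:1 (3.1, 5.2). Creatinine preoperatively and at 24 and 48 h (7.1). Between-arm t-test or Wilcoxon-Mann-Whitney on the change (13.1).

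**Inputs assumed.** The documents give no dialysis rate, creatinine rise, creatinine SD or post-dialysis value, and no alpha. All are assumptions here, with two-sided 5% throughout.

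**The plan's own figure.** Sections 5.3 and 13.2 claim 80% power for a difference of roughly 1 SD with n=30. At 15 per arm the normal approximation gives 78% and the exact noncentral t gives 75%. Given the word 'roughly', that reproduces. It concerns the primary outcome and is not in dispute here.

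**Chance that the issue arises.** With a per-patient rate r of dialysis starting before a draw, P(at least one among 30) = 1 - (1 - r)^30.

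| r (assumed) | Calculation | Chance |
|---|---|---|
| 0.25% | 1 - 0.9975^30 | 7% |
| 0.5% | 1 - 0.995^30 | 14% |
| 1% | 1 - 0.99^30 | 26% |

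**Effect of one such patient.** Assume mean creatinine rises of 0.35 v 0.10 mg/dL, SD 0.3, 15 per arm, and one dialysed patient recorded at -0.2 mg/dL. Simulated Wilcoxon-Mann-Whitney power:

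| Dialysed patient | As recorded | Ranked worst |
|---|---|---|
| None | 56% | not applicable |
| One, in the worse arm | 40% | 64% |
| One, in the better arm by chance | 63% | 35% |

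**Attenuation or reversal.** Replacing an expected 0.35 by -0.2 in one of 15 patients moves that arm's mean by (0.35 + 0.2)/15 = 0.037 mg/dL. The expected difference falls from 0.25 to 0.213 mg/dL and keeps its sign. In 8,000 simulated trials the worse arm had the lower mean in 1.0% without a dialysed patient and in 2.3% with one. A significant result in the wrong direction occurred in none.

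**Sensitivity to the assumptions.** Take a true difference of 1 SD instead, with one dialysed patient in the worse arm. Power is about 72% with no dialysed patient. It is 65% if dialysis brings that patient to the other arm's mean change, and 55% if it brings the patient 1 SD below that mean. Ranked worst, it is 78%.

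**Does the separate dialysis test cover this?** At 15 per arm, Fisher's exact test gives p = 1.00 for 1 v 0, 0.48 for 2 v 0, 0.22 for 3 v 0, 0.10 for 4 v 0 and 0.042 for 5 v 0. One or two dialysed patients cannot produce a significant result there, although one is enough to move the creatinine comparison.

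**The case against.** The best case for leaving the plan alone is that this may never happen. Emergency surgery, moderate to severe prior kidney injury and imminent need of dialysis are all excluded, and only dialysis begun before a 24 or 48 h draw matters. Dialysis is reported by arm in its own right, so kidney failure is not hidden. The outcome is secondary, in a 30-patient biomarker study. All of this stands and limits the weight. None of it supplies a handling rule.

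A second objection is that ranking worst is only one option and does not always raise power. This also stands: if the dialysed patient is in the better arm by chance, power falls to 35%, against 63% as recorded. The argument for ranking worst is that it orders patients by renal outcome, not that it makes significance more likely. This is why the as-recorded analysis should be kept beside it.

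A reader might infer three stronger things, which the documents do not support:

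- **That the arm with more kidney failure would come out ahead on creatinine.** The calculation shows a diluted difference, with no significant reversal.
- **That chloride and pH are biased in the same way.** The plan names no favourable direction for either, and pH is measured at 24 h only. Values after dialysis may be masked by treatment, but they cannot be called falsely good.
- **That a case is likely.** Rates of 1% to 5% would give 26% to 79%, but if these are rates of any dialysis before discharge, the result counts patients whose dialysis began after both draws.

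**Conclusion.** The gap is real for creatinine. Followed as written, 13.1 uses values that dialysis has lowered, and the listed data would not show which values those are. The bias favours the arm of the dialysed patient. Its likely form is attenuation: in the main illustration, power drops from 56% to 40% when one dialysed patient falls in the worse arm.

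That size rests entirely on assumed rises, SD, post-dialysis value and dialysis rate. It is also conditional on an event with a 7% to 26% chance if the rate before a draw is 0.25% to 1%. Nothing here shows an effect on the primary outcome or its sample size. This is a cheap improvement to a secondary outcome, worth making before data collection because the start time may not be recoverable later.

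**What to change.** - **12.1:** add the date and time of first dialysis to the data taken from the chart.
- **13.1, creatinine:** state that a patient who starts dialysis before the 24 h or 48 h sample is ranked worst at that timepoint, using the Wilcoxon-Mann-Whitney test already planned. Give the as-recorded analysis as a sensitivity analysis and report the number affected per arm.
- **13.1, chloride and 24 h pH:** keep the values as recorded, flag those drawn after dialysis, and repeat the comparison without them as a sensitivity analysis. Carrying forward the last value before dialysis is not advised, because it would replace the 24 or 48 h outcome that 7.1 defines with an earlier one.

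The cost is one chart item and a few sentences. Treatment and sampling do not change. The downside is that the creatinine result becomes a rank comparison whenever such a patient occurs. If nobody is dialysed before a draw, the results are the same as under the present text.

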- 3.1. This is a prospective, open-label, randomized, single center, controlled clinical study to determine the effect of intraoperative infusion of NS versus Isolyte on post-cardiac surgery on AKI event (renal injury) as measured by urinary [TIMP-2]*[IGFBP7] levels. After informed consent, we will randomly assign 30 trial-completing participants (potentially enrolling up to 40 to account for any dropouts) to the two study arms in a 1:1 ratio. We will compare the effect of electrolyte solution on patients' post- vs. preoperative [TIMP-2]*[IGFBP7] score differences with pairwise t-tests, and will similarly analyze routine demographic data and potential confounders, as well as secondary outcomes as listed below.
- 3.2. This is an open-label trial.

4. Inclusion and Exclusion Criteria

- 4.1. Participants will be drawn from the population of adult patients undergoing cardiac surgery at UNMH.

The Impact of Low Chloride Containing Fluids on Acute Kidney Injury after Cardiopulmonary Bypass as Assayed by Urinary [TIMP2]*[IGFBP7]

- 4.2. Inclusion criteria: consenting adult male and female patients undergoing non-emergent on- and off-pump cardiac surgery including: bypass grafting, valvular procedures, congenital defect correction, and thoracic aortic procedures or a combination of these procedures.

Exclusion criteria: emergency surgery, pregnancy, previous renal transplantation, documented moderate to severe AKI prior to enrollment (e.g. RIFLE-I or RIFLE-F/KDIGO stage 2 or 3), patients already receiving dialysis (acute or chronic) or in imminent need of dialysis at time of enrollment, subjects with chronic kidney disease without baseline serum creatinine value (baseline within 6 months of enrollment).

- 4.3. This study does not involve adults unable to consent, individuals who are not yet adults, pregnant women, or prisoners.
- 4.4. We will not exclude particular populations such as women, children, persons not fluent in English, any particular racial or ethnic groups, etc.

5. Number of Subjects

- 5.1. This is not a multicenter study; all recruitment will occur at UNMH.
- 5.2. We plan to recruit sufficient participants to obtain complete data on 30 subjects (15/group). We do not anticipate a high withdrawal rate, but may recruit as many as 40 to have a complete dataset of this size. Recruitment will stop upon attainment of the full sample of 30, or with the 40th consenting patient who at least begins study treatment (whichever comes first).

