- Both normal saline and Isolyte-S (B Braun Medical Inc., Bethlehem PA, USA) are legally marketed in the United States, and FDA approved for this indication (fluid maintenance). Providers already have clinical discretion to administer either normal saline or Isolyte-S in the setting of cardiac surgery, and it is normal practice to administer electrolyte-containing fluids intravenously during these surgeries.
 - Subjects will not be asked to complete a questionnaire or otherwise volunteer information.
 - All study data will be sourced from patient medical records, except for the TIMP2 and IGFBP7 laboratory values.
 - The preoperative serum creatinine test is part of routine practice, and is expected for all preoperative cardiac surgery patients. Intraoperative fluid maintenance is routine for surgical patients, and providers already have clinical discretion to administer normal saline or Isolyte-S. Arterial blood pH monitoring is also routine for these patients. The remaining data consists of laboratory values. Routine labwork (including all of the lab-based secondary outcome measures) is an expected part of cardiac surgery patients' postoperative care. The TIMP2*IGFBP7 index will be obtained in addition to routine postoperative monitoring; routine postoperative labwork (e.g. to assess kidney function) is not being replaced.
 - This is not a humanitarian-use device study.
 - There will be an interim review of all study data after completion of the 20th participant, in an effort to detect any unusual patterns of morbidity/mortality. All outcomes will be analyzed. The study will be suspended if this interim review detects a statistically-significant difference is detected between study arms with respect to the clinically-determined need for dialysis prior to discharge.

13.Data Analysis

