- 14.5. The study will be suspended if a statistically-significant difference is detected in the interim analysis between study arms with respect to the clinically-determined need for dialysis prior to discharge.
- 14.6. The HRRC will be notified if the suspension criterion is met.

15. Withdrawal of Subjects

- 15.1. We have not identified any likely circumstances in which subjects may be withdrawn from the study without their consent. However, there is a very unlikely chance (<1%) of an unforeseen situation in the process of administering the fluids that may bias the results; data for any affected patients would be omitted from the final analysis.
- 15.2. Consenting participants may withdraw at any time. If medically appropriate in the clinical judgment of the attending physicians, the IV fluid solution may be changed upon participant-initiated withdrawal. This change would not require any tapering of dosage or laboratory tests. Data collection would simply cease.
- 15.3. We do not anticipate any partial withdrawals from arm assignment only, but participants who wish to withdraw from arm assignment and for whom the IV fluid is changed per the providers' clinical judgment will also be removed from data collection efforts in order to maintain data consistency. If an enrolled patient elects this type of partial withdrawal after IV fluid administration begins and the fluid is not changed per the providers' clinical judgment, data collection will continue as usual because there is no effective change to treatment. After arm assignment, details of the administration of IV fluids (e.g. flow rate, duration, etc) are always left to the discretion of the attending physicians, so post-withdrawal IV fluid administration will not change in a specified way.
- 15.4. Data for participants who elect to withdraw completely will be omitted from analysis. Any already-gathered data will be maintained for purposes of safety review and oversight, but identifiers will be removed upon withdrawal. Specimens will be appropriately discarded upon patient withdrawal regardless of data collection status.

15.5. Participants who elect to withdraw simply need to say so to an investigator.

16.Data Management/Confidentiality

- 16.1. The research team will use their HSC-granted access to PowerChart to access patient medical records to obtain the data listed in this protocol, and also obtain data from laboratory values.

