safety of normal saline vs. Isolyte for cardiac surgery patients, or the extent to which they may or may not reduce kidney-related complications of surgery.

- 18.2. Both normal saline and Isolyte are in widespread use for fluid replenishment during surgery, with excellent safety records.
- 18.3. Risks to embryos and fetuses are not relevant here; pregnancy is an exclusion criterion.
- 18.4. There are no appreciable risks to others who are not subjects.
- 18.5. Steps taken to minimize the probability or magnitude of risks include: selection of FDA-approved IV fluids for the study, the open-label nature of the study, permitting provider discretion in amounts administered, gathering as much study data as possible from the already-existing medical record, maintaining routine labwork to forewarn providers of developing kidney problems, and exclusion of patients known to have kidney problems.

19. Potential Benefits to Subjects

- 19.1. We have not identified any benefits that will accrue to all subjects. If one of the two IV fluids is superior to the other, patients randomized to receive it may experience benefit. The existence and nature of these benefits is not currently known, but because both normal saline and Isolyte are currently in widespread use for intraoperative fluid maintenance without known major problems, any benefit is expected to be small and only detectable at the group level.

20. Recruitment Methods

- 20.1. Potential subjects who are already inpatients will be recruited in patient rooms at UNMH the night before surgery. For patients who arrive at the hospital on the day of surgery, recruitment will occur in the pre-operative holding areas.
- 20.2. Investigators will identify potential subjects from their regularly-scheduled case load, and apply the inclusion/exclusion criteria to the extent possible prior to making research-related contact with a patient.
- 20.3. No recruitment materials are planned. Potential participants will be provided a copy of the consent form for their review and consideration during the recruitment process. Consenting participants will be provided a copy of the completed form.

21. Provisions to Protect the Privacy Interests of Subjects

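### Does testing the primary index by arm at patient 20, with an interim rule for dialysis only, put the final result at risk?

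*Combined protocol and SAP*

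**What the plan says.** Section 12.1 schedules one interim review after the 20th participant completes, to look for unusual morbidity or mortality, and adds: "All outcomes will be analyzed". Section 14.1 gives the task to the principal investigator and co-investigators, "upon completion of data collection for the 20th participant, in an effort to detect substantial differences in outcomes". Section 14.4 is the most explicit: "In addition, all outcomes will be analyzed with the above-described statistical tests". The tests meant are those of 13.1: a t-test or Wilcoxon-Mann-Whitney test for the index and the laboratory outcomes, and Fisher's exact test for dialysis.

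One consequence is stated, in 12.1 and again in 14.5: "The study will be suspended if a statistically-significant difference is detected in the interim analysis between study arms" in the need for dialysis before discharge. Section 14.6 adds notice to the HRRC. No boundary or rule is attached to the index.

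The end of recruitment is set in 5.2 without reference to any result: "Recruitment will stop upon attainment of the full sample of 30, or with the 40th consenting patient who at least begins study treatment".

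**The concern.** Two things look wrong. First, the primary hypothesis is tested at two-thirds of the sample with the same unadjusted test that will be used at the end, and no sentence says that the interim result cannot be reported as a finding. Two unadjusted chances at p<0.05 would raise the false-positive rate above 5%.

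Second, the people who see the result also run the rest of the trial. Under 20.2, "Investigators will identify potential subjects from their regularly-scheduled case load, and apply the inclusion/exclusion criteria to the extent possible". Under 15.1, if an unforeseen event during fluid administration may bias the results, "data for any affected patients would be omitted from the final analysis". The choice between t-test and Wilcoxon-Mann-Whitney in 13.1 also rests on a normality judgement with no stated criterion. Knowing which arm leads on the primary outcome could colour any of these decisions in the last third of the trial.

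An early result is also fragile. Section 19.1 says "any benefit is expected to be small and only detectable at the group level", and when the true effect is small many significant interim results will not survive to the final test.

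**Working it through.** **Inputs.** 15 completers per arm (5.2); interim at 20 completers, taken as 10 per arm; design difference of about 1 SD with 80% power (5.3, 13.2). Alpha and sidedness are not stated; two-sided 0.05 is assumed throughout.

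**The plan's own figure.** Normal approximation: power = Φ(d√(n/2) − 1.96) = Φ(1 × √7.5 − 1.96) = Φ(0.779) = 78.2%, close to the stated 80%. The exact t-test gives 75.3%. Sections 5.3 and 13.2 both attach this power to the planned sample of 30, with no allowance for a second test.

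**Type I error under the plan as written.** The index cannot stop the trial or end recruitment, so only the final test decides: 5.0%.

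**Type I error if an interim p<0.05 were also claimed.** By simulation (400,000 trials, t-tests at 10 and 15 per arm), 55.7% of significant interim results under no effect are not significant at the end. The added error is 0.050 × 0.557 = 0.028, and 0.050 + 0.028 = 0.078. The bivariate normal with correlation √(20/30) gives 7.7%. A 7/13 split at the interim gives 8.0%; Wilcoxon-Mann-Whitney gives 7.0%.

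**What the interim test would show.** The chance that the better arm is ahead is Φ(d√(10×10/20)) = Φ(2.236d). The last column is the second multiplied by the fourth.

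| True effect | Interim p<0.05 | Better arm ahead | Significant interim result lost at final | Both: significant, then lost |
|---|---|---|---|---|
| none | 5.0% | – | 55.7% | 2.8% |
| 0.3 SD | 9.7% | 74.9% | 37.4% | 3.6% |
| 0.5 SD | 18.5% | 86.8% | 23.6% | 4.4% |
| 1 SD | 56.2% | 98.7% | 4.8% | 2.7% |

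The reversal percentages are high for small effects, but they are conditional on interim significance. Across all trials a reversal happens in 2.7% to 4.4%. If the final test governs, each reversal is simply an early result that was never used.

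**Does the plan leave a claim open?** Section 6.1 places completion of all analyses, and submission, after data collection ends. Section 15.1 speaks of a final analysis. Section 28.1 recognises that preliminary results from a small sample are less reliable. None of these forbids an interim claim outright, but they all point to the full sample, and no section points the other way.

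**How much the 15.1 route could carry.** The protocol puts such events below 1%. At most 40 − 20 = 20 patients are still to be treated after the interim, so fewer than 0.2 patients are expected to be affected.

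**What dropping the index would cost.** With 10 per arm, Fisher's two-sided p for 4 v 0 dialysis events is 2 × 210/4,845 = 0.087, and for 5 v 0 it is 2 × 252/15,504 = 0.033. With no events in one arm, the suspension rule therefore needs five in the other. Section 12.1 describes the outcome measures as indicators of kidney injury or its risk, and 7.2 names no separate safety endpoints. The index is thus one of the few kidney signals the review has.

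**The case for a change.** The strongest case for a change is that a scheduled by-arm p-value for the primary outcome, with no rule attached, is an avoidable loose end. Randomisation protects assignment but not later discretion. The reviewers are unblinded and not independent, and one sentence would settle that the primary conclusion comes from the final sample. That sentence would cost no patients, data or power.

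The description of the plan is correct, and no sentence expressly bars an interim claim. The sentence would do no harm, but it would only write down what 5.2, 5.3, 6.1 and 14.5 already imply, and it would alter no result.

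The case for removing the index is weaker. The trial is open-label, so the arm is known whenever an omission is judged, with or without an interim test. A co-investigator's laboratory runs the assays (8.3), so informal knowledge of the trend would remain. By-arm creatinine, which 2.1 treats as the reference measure for AKI, would still show which arm leads on kidney function. It is true that 27.1 calls the index not yet validated, which lowers its value as a safety signal, but a review that otherwise depends on a 5 v 0 dialysis split has little to spare. A formal efficacy boundary (interim p<0.001, final 0.05) would hold type I error at 5.0% and power at 1 SD at about 75%, but it would create an early-claim route that the plan does not contain.

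**Conclusion.** No change follows. The interim index test is an unadjusted look that feeds no decision, inside a review whose stated purpose is safety. Followed as written, the plan keeps type I error at 5.0% and leaves power at 15 per arm untouched. The figure of about 7.8% (7.0% to 8.0% across the variants tried) describes conduct for which the protocol makes no provision. It rests on two-sided 0.05 and an interim at or near 10 per arm. What remains is possible influence on an unblinded team. Its size cannot be derived from the documents, and the one route with a stated frequency amounts to fewer than 0.2 expected patients. Keeping a kidney-injury marker in the safety review in exchange for that is a fair trade-off, and an analyst would take the 13.1 test on the final sample as the primary result without being told.

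### Sections 15.1 and 15.3 drop randomised patients on open-ended or treatment-received grounds, and section 13.1 states no as-randomised analysis set; the expected effect is small and the repair is mostly wording

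*Combined protocol and SAP*

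**What the plan says.** All references are to the combined protocol and SAP.

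- **15.1** accepts that "there is a very unlikely chance (<1%) of an unforeseen situation in the process of administering the fluids that may bias the results", and provides that "data for any affected patients would be omitted from the final analysis".
- **15.3** deals with participants who withdraw from arm assignment only. Those whose fluid is then changed on the provider's judgement "will also be removed from data collection efforts in order to maintain data consistency". Those whose fluid is not changed stay in. No such withdrawals are anticipated.
- **15.4** states: "Data for participants who elect to withdraw completely will be omitted from analysis". It adds: "Any already-gathered data will be maintained for purposes of safety review and oversight, but identifiers will be removed upon withdrawal". Specimens are discarded at withdrawal.
- **13.1** defines the endpoint ("the difference between pre- and postoperative index values will be recorded as the primary outcome") and the tests, but not which patients enter them. No section says that patients are analysed as randomised, and no sensitivity analysis is planned.
- **3.2** makes the trial open-label. **5.2** targets 30 patients with complete data, 15 per group, recruiting up to 40, and does not expect a high withdrawal rate.
- **14.1** says that the PI and "co-investigators will conduct an interim review of patient records upon completion of data collection for the 20th participant". **14.4** adds: "In addition, all outcomes will be analyzed with the above-described statistical tests".

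**The concern.** Randomisation protects the comparison only while patients are kept or lost for reasons that do not depend jointly on arm and outcome. Section 15.1 hands that decision to an unnamed person, at an unstated time, on the test of whether an event might bias the results, which is itself a judgement about the results. Arm is known throughout. From the 20th participant on, the investigators will also have analysed every outcome, so nothing in the text stops an omission from being decided with both in view.

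Section 15.3 makes inclusion depend on the fluid actually received. That is per-protocol logic, and because 13.1 defines no analysis set, it governs the only analysis there is.

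With 15 per arm, one to three patients carry real weight. If losses differ by arm and relate to the index, the comparison of those who remain is biased. If they do not differ by arm, type I error is not inflated.

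**Working it through.** **The plan's own figure.** Sections 5.3 and 13.2 give 80% power for a difference of about 1 SD with n = 30. Alpha and sidedness are not stated; I assume 0.05.

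- Noncentrality = 1/√(1/15 + 1/15) = 2.739.
- Two-sided normal approximation: Φ(2.739 − 1.960) = 78.2%.
- Exact t-test: 75.3% two-sided, 84.8% one-sided.
- Two-sided 80% power is reached at 1.06 SD, which the plan's approximate wording covers.

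The point does not depend on this figure; 75% is the reference power below.

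**Step 1: how often 15.1 would apply.** The figure below 1% can be read in two ways.

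- *Per patient, at its 1% ceiling (assumption).* P(at least one) = 1 − 0.99^n: 26.0% for n = 30 and 33.1% for n = 40.
- *For the study as a whole.* The chance of any such situation is below 1%.

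Binomial probabilities under the per-patient reading:

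| Omissions | n = 30 | n = 40 |
|---|---|---|
| 0 | 74.0% | 66.9% |
| 1 | 22.4% | 27.0% |
| 2 | 3.3% | 5.3% |
| 3 or more | 0.3% | 0.7% |

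**Step 2: what a one-arm loss does if it happens.** Assumptions: no true effect, standard normal outcomes, two-sided pooled t-test at 0.05. Draw 15 + k patients in one arm, remove the k with the largest loss score r × outcome + √(1 − r²) × noise, and compare with an intact arm of 15 (200,000 runs each). Entries are bias in SD and type I error.

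| Loss-outcome link | k = 1 | k = 2 | k = 3 |
|---|---|---|---|
| r = 0 | 0; 5% | 0; 5% | 0; 5% |
| r = 0.3 | 0.04; 5.1% | 0.06; 5.4% | 0.08; 5.7% |
| r = 0.5 | 0.06; 5.4% | 0.10; 6.2% | 0.14; 7.0% |
| Exactly the worst values | 0.12; 7.0% | 0.21; 10.5% | 0.28; 14.7% |

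**Step 3: weight Step 2 by Step 1.** Average type I error = 5% + Σ P(k) × (type I at k − 5%). Every omission is placed in the same arm, and three or more are counted as three.

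- r = 0.3, n = 40: 5 + 0.270×0.1 + 0.053×0.4 + 0.007×0.7 = 5.05%. For n = 30: 5.04%.
- r = 0.5, n = 40: 5 + 0.270×0.4 + 0.053×1.2 + 0.007×2.0 = 5.19%. For n = 30: 5.14%.
- Worst values, n = 40: 5 + 0.270×2.0 + 0.053×5.5 + 0.007×9.7 = 5.9%. For n = 30: 5.7%.

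Under the whole-study reading, one worst-value omission with probability 1% gives 5 + 0.01×2.0 = 5.02%.

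**Step 4: what retaining patients costs.** Suppose the true effect is 1 SD and k of 15 patients in the better arm lose a fraction f of it. The estimate becomes 1 − k×f/15.

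| k | f | Estimate (SD) | Power |
|---|---|---|---|
| 0 | – | 1.00 | 75% |
| 1 | 0.5 | 0.97 | 72% |
| 1 | 1 | 0.93 | 68% |
| 3 | 1 | 0.80 | 53% |

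With no true effect, type I error stays at 5%.

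**The case against.** The strongest reply is that these events are rare and the effect trivial. The protocol puts 15.1 situations below 1%, anticipates no 15.3 cases, and expects no high withdrawal rate. Step 3 bears this out, and that part of the objection stands: it limits the size of the point. It does not supply the missing rule. The rates are expectations, not caps, and no section requires losses to be reported by arm, so a reader could not tell harmless loss from selective loss.

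Four stronger readings are tempting, and the documents do not support them.

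- **That false positives run at 7-15%.** Those figures hold only if one to three of the very worst outcomes are in fact lost from one arm. Three or more 15.1 omissions have a probability of 0.3-0.7% even at 1% per patient.
- **That omissions are meant to be chosen on outcome.** The 15.1 trigger arises while fluid is being given, before the 24 h index exists, and the review at the 20th participant is described as a search for unusual morbidity and mortality. The gap is only that the time of the decision is not fixed.
- **That 15.3 removals can respond to the primary result.** Section 7.2 says that laboratory values arrive too late to change the fluid.
- **That 15.4 is itself a fault, or that 5.2 licenses discarding ten patients.** Stopping collection when consent is withdrawn is proper, and whether data already gathered may be used depends on consent terms not available here. Section 5.2 is a recruitment rule; 40 against 30 is a ceiling, not a forecast.

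**Conclusion.** The point holds as a modest one. Section 15.1 leaves omission open to unblinded judgement, 15.3 excludes by fluid received, and 13.1 does not say that patients are analysed in the arm assigned. The expected damage from 15.1 is an average type I error of about 5.0-5.2% under plausible links between loss and outcome, and at most about 5.9% under the worst link. This rests on 1% per patient, all omissions in one arm, normal outcomes and a two-sided 0.05 test. If the stated rate applies to the whole study, the effect is negligible. The documents give no rate for 15.4, so its contribution cannot be sized. The case for acting is that an avoidable route to bias can be closed at very little cost.

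**What to change.** - **13.1:** add *The primary analysis includes all randomised patients who began study fluid and have baseline and 24 h index values, in the arm assigned, whatever fluid they received.*
- **15.1:** replace omission with *recorded as a deviation, kept in the primary analysis, excluded only in a sensitivity analysis.*
- **15.3:** continue the 24 h urine sample and routine data collection after a fluid change, unless the participant withdraws consent for data use.
- **15.4:** complete withdrawals may stay omitted where consent requires, but are counted by arm.
- **Reporting:** give all losses by arm and reason.

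The cost is protocol wording, a loss table and 24 h assays on the few patients otherwise dropped. The statistical downside is the dilution in Step 4, which the sensitivity analysis lets a reader judge. The sample target, the cap of 40, the tests and clinical care do not change. The proposed set still requires a 24 h value, so it does not recover patients without one and is not a full intention-to-treat analysis.
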